RESEARCH PROTOCOL

Title of project: Dipyridamole Assessment for Flare REduction in SLE: The DARE study

Principal Investigator: [name]

Co-Investigator: [name]

Co-Investigator: [name], PhD

Co-Investigator: [name]

Co-Investigator: [name]

Co-Investigator: [name], PA-C

Consultant: [name].

Abstract

T cells in systemic lupus erythematosus (SLE) express an abnormal phenotype characterized by increased effector functions and deficient regulatory responses. Dipyridamole, a phosphodiesterase inhibitor extensively used in combination with low dose aspirin in secondary stroke prevention, has been proposed as a specific T cell directed treatment for SLE. Dipyridamole inhibits the calcium/calcineurin/NF-AT pathway in SLE T cells *in vitro* and abrogates expression of cytokines and costimulatory molecules, eventually also affecting B cell responses. Dipyridamole delays the emergence of lupus related pathology in lupus prone mice, but has not yet been studied in humans with SLE. We aim to investigate the efficacy of dipyridamole in the prevention of flares in SLE patients after withdrawal of background immunosuppressive medications. We will additionally evaluate the safety and tolerability of dipyridamole and its impact on quality of life measures in this population. Furthermore, the effect of dipyridamole on T and B cell biomarkers will be examined.

A. Specific aims

Primary objective: To examine the efficacy of dipyridamole/aspirin (Aggrenox, Boehringer Ingelheim Pharmaceuticals, Inc.) for flare prevention in patients with SLE as measured by the BICLA endpoint (improvement in disease activity compared to baseline without new flare or additional treatments).

Secondary objectives: To examine the effect of dipyridamole on:

1. Flare rate and time to first flare
2. Systemic response index (SRI) 4/5 at week 24, BICLA and SRI 4/5 at each month, SRI component analyses, CLASI and DIAL responses

3. Patient reported outcomes, including: health related quality of life (measured by the Lupus QoL, LupusPRO and the Short Form 36v2), fatigue (measured by the FACIT-fatigue score), sleep quality (measured by the Pittsburgh Sleep Quality Index (PSQI)) and depression (measured by the Center for Epidemiologic Studies Depression (CES-D) Scale)
4. Tolerability and safety

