This is a prospective placebo-controlled randomized study. Patients will enter with active disease. After informed consent and screening procedures are completed, enrolled patients may be optionally treated with intramuscular methylprednisolone acetate and background immune-suppressive medications will be withdrawn. Injection of methylprednisolone acetate may be repeated in week 2 at the discretion of the investigator, to induce a state of remission/low disease activity. Patients will be assigned to begin the study medication upon enrollment (baseline, week 0). Patients will be randomized 1:1 to Aggrenox or half of an 81mg aspirin tablet twice daily for 24 weeks. Aggrenox will be initiated at a single bedtime dose for a week, followed by twice daily administration for the rest of the study, to minimize the risk of side effects (e.g. dizziness, headache). Aspirin will be titrated similarly to preserve blinding. Gelatin capsules will be used to cover the pills in order to preserve the blinding.

Participants will be evaluated at baseline (week 0), week 2, week 4 and every 4 weeks until the completion of the study at week 24. An additional study visit may be scheduled at the time of a clinically significant flare (flare visit). Evaluation of general health status, adverse events and lupus disease activity (SLEDAI, BILAG, PGA, CLASI, DIAL, SF-36v2, Lupus QoL, FACIT-fatigue, PSQI, CES-D) will be performed at baseline, week 4 and every subsequent visit. Time to first flare and severity of first flare will be examined. At the time of a clinically significant flare

(defined as at least one BILAG letter grade increase or an increase of ≥ 3 points in SLEDAI AND clinician determination of clinically significant deterioration) patients may elect further treatment with intramuscular methylprednisolone acetate or, if necessary DMARD therapy, but will continue the study as permanent nonresponders.

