Patients will have CBC with differential, metabolic profile, urinalysis, anti-dsDNA, and complement studies performed at baseline, each of the subsequent monthly visits through week 24 and the flare visit. If urine dipstick is $\geq 2+$, a protein/creatinine ratio will be performed at the following visit (or sooner at the discretion of the investigator). Pharmacodynamic and exploratory blood and urine biomarker samples will be drawn prior to first dose at baseline, at weeks 8 or 12, week 24 and at the flare visit. Some of the stimulated cell gene expression and signaling pathway work will be performed on deidentified samples in collaboration with Drs. [name] and [name] at Beth Israel Medical Center in Boston Massachusetts. We will have a material transfer agreement with that institution. In the context of our ancillary study of heart rate variability in lupus, a 5-minute ECG will be performed at each monthly visit and at the flare visit (please see attached protocol).

Summary of Medications and Medication Changes

At screening, participants may be receiving daily prednisone at a dose of 20mg or less, and/or one or more of the following DMARDs: hydroxychloroquine, methotrexate, azathioprine and mycophenolate mofetil, and must be agreeable to discontinue their background immune suppressants upon enrollment. Patients taking hydroxychloroquine upon enrollment will however continue the medication throughout the study.

All participants may be administered optional intramuscular methylprednisolone acetate upon enrollment (usually 160mg, but dose may adjusted based on clinical judgment). Intramuscular steroid treatment may be repeated at weeks 2 at the discretion of the investigator, to induce a state of remission/low disease activity while background medications are withdrawn. Patients on oral steroids will be given an optional rapid taper over 3-4 weeks.

Duration of participation

Participants will receive treatment for a total of 24 weeks.

Patient enrollment

A maximum of 50 patients meeting the inclusion criteria and not meeting the exclusion criteria will be enrolled in the study. The enrollment period is expected to last for at least 18 months but could last as long as four years.

Data collection and analysis

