Biologic Endpoints: Changes in B cell and T cell subsets, relevant gene expression patterns, B-T cytokine profiles and cell-bound complement split products and urinary biomarkers at baseline versus week 24 in each treatment group. Evaluation of B Cell/T cell expression patterns in patients with higher versus lower IL6, IL17 and IL23 expression detected at baseline. These endpoints will be evaluated both as changes with Aggrenox versus aspirin treatment (non parametric analysis) and as components of multivariate modeling and propensity score analysis as described above. An exploratory responder analysis will also be performed (changes in these biomarkers with response versus non-response in patients receiving Aggrenox). The latter analysis may need to be observational only, as it is likely to be underpowered and diluted by patients who may not have begun the trial with the characteristic abnormalities in T cell subset activity.

Power/Sample size calculation

We base this calculation on preliminary data from the BOLD study (11) which is an exploration of underlying biology in patients with SLE who receive steroids and are withdrawn from background treatments, in other words identical to the aspirin group in the current proposal. To date we have analyzed data from 31 patients who completed the BOLD protocol and these outcomes suggest that no more than 20% of the aspirin group will achieve a BICLA response at week 16 (range 1-20%) and no more than 5% achieves a BICLA response at week 24 (range 0-10%). Assuming a 35 to 50% response rate in the Aggrenox group at week 24, a sample size of 50 patients will provide a power around 80% at a significance level of 0.05 at week 24. By these settings and assumptions, the following power estimates are obtained.

Power calculations for a 50 patient study, if alpha=0.05 with response rates:

	Rate 1	Rate 2	Rate 3	Rate 4	Rate 5	Rate 6	Rate 7
Aggrenox n=25	60%	55%	50%	45%	40%	35%	35%
Aspirin n=25	20%	15%	10%	10%	5%	5%	3%
power	0.84	0.86	0.89	0.80	0.86	0.77	0.84

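### The aspirin response rate behind the power statement comes from 31 BOLD completers called identical to the aspirin arm; they are not, and power falls to 0.57 inside the plan's own ranges

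*Combined protocol and SAP*

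**What the plan says.** Section E, Power/Sample size calculation, rests on BOLD: "To date we have analyzed data from 31 patients who completed the BOLD protocol". It describes BOLD patients as those "who receive steroids and are withdrawn from background treatments, in other words identical to the aspirin group in the current proposal". From them it puts the aspirin BICLA rate at week 24 at 5% at most, with a range of 0 to 10%. It assumes 35 to 50% on Aggrenox and concludes that "a sample size of 50 patients will provide a power around 80% at a significance level of 0.05 at week 24". Seven pairs of rates follow, with power from 0.77 to 0.89.

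Other sections describe the aspirin arm differently:

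- Section D, Research design and Methods: "enrolled patients may be optionally treated with intramuscular methylprednisolone acetate".
- Section D, Summary of Medications and Medication Changes: patients may (not must) be on prednisone or a listed DMARD at screening, and the oral steroid taper is optional. Hydroxychloroquine is one of the listed DMARDs, but "Patients taking hydroxychloroquine upon enrollment will however continue the medication throughout the study".
- Section G, Inclusion Criteria: active disease despite standard of care is required. No criterion asks for a drug that will be stopped.

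Section C describes BOLD as using a short parenteral steroid course while background drugs were withdrawn.

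**The concern.** The aspirin rate is the input to which the power is most exposed, and its only stated support is that BOLD patients match the aspirin arm. Under the protocol's rules, a patient taking only hydroxychloroquine, or no listed drug, can be enrolled with nothing withdrawn and no steroid given. That patient counts fully in the primary two by two table. The premise for borrowing the rate therefore conflicts with the treatment rules.

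The rate is also stated more firmly than 31 patients allow. If the true aspirin rate is nearer 10% than 5%, the study is much weaker against the lower Aggrenox rates it assumes, and the power table does not show this.

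**Working it through.** **1. Set BOLD, as the protocol describes it, beside the aspirin arm.**

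| Feature | BOLD (sections C and E) | Aspirin arm (sections D and G) |
|---|---|---|
| Steroid | received | injection optional; oral taper optional |
| Background drugs | withdrawn | withdrawn if taken; hydroxychloroquine kept |
| Withdrawable drug needed at entry | not stated | no |

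The steroid difference is explicit. The other differences are with BOLD as described here; its entry criteria and hydroxychloroquine rule are not given.

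**2. Reproduce the power table.** Inputs from section E: 25 per arm, alpha 0.05. Sidedness and method are not stated. A two-sided pooled normal approximation without continuity correction fits:

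Power = Φ{ [ |p1 − p2| − 1.96·√(2·p̄(1 − p̄)/25) ] / √[ (p1(1 − p1) + p2(1 − p2))/25 ] }, with p̄ = (p1 + p2)/2.

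For 35% vs 5%: (0.300 − 0.2217)/0.1049 = 0.746, power 0.77 (stated 0.77). The seven pairs give 0.845, 0.866, 0.895, 0.811, 0.865, 0.772 and 0.844, against 0.84, 0.86, 0.89, 0.80, 0.86, 0.77 and 0.84. The arithmetic of the table is sound.

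**3. Precision of the BOLD rate.** The responder count is not given. An observed rate of 5% or less in 31 patients means 0 or 1 responder, since 2/31 = 6.5%. Exact (Clopper-Pearson) two-sided 95% limits:

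- 0/31: upper limit 1 − 0.025^(1/31) = 11.2%.
- 1/31 (3.2%): 0.1% to 16.7%.

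**4. Power over the plan's own ranges and up to those limits**, same formula, 25 per arm:

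| Aspirin rate | Aggrenox 35% | 40% | 45% | 50% |
|---|---|---|---|---|
| 5% | 0.77 | 0.86 | 0.93 | 0.97 |
| 10% (top of plan's range) | 0.57 | 0.70 | 0.81 | 0.90 |
| 11.2% (upper limit, 0/31) | 0.52 | 0.65 | 0.77 | 0.87 |
| 16.7% (upper limit, 1/31) | 0.31 | 0.45 | 0.59 | 0.72 |

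For 35% vs 10%: (0.250 − 0.2315)/0.1127 = 0.164, power 0.57. For 40% vs 10%: (0.300 − 0.2400)/0.1149 = 0.522, power 0.70.

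**5. What the plan's table shows.** Aspirin rates of 10, 15 and 20% appear only with Aggrenox rates of 45, 50, 55 or 60%. The pairings 35% vs 10% and 40% vs 10% lie within the stated assumptions but are absent. For 80% power by the same method, 35% vs 5% needs 27 per arm and 35% vs 10% needs 43.

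**The case against.** The plan does not hide uncertainty about the aspirin rate. It gives a range, tabulates rates from 3 to 20%, calls the trial a pilot, would accept a non-significant 12-point difference as grounds for a larger study, and allows sample size to be discussed at the interim analysis. This lowers the stakes. It does not repair the claimed match with BOLD or supply the missing pairings.

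Two technical replies have some force. If a higher aspirin rate came with an equally higher Aggrenox rate, keeping a 30-point difference, power would fall only from 0.77 to 0.70 at an aspirin rate of 10%. And a one-sided 95% limit at 0/31 is 1 − 0.05^(1/31) = 9.2%, so with no responders the 10% bound is borderline. The 5% ceiling fails either way.

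Three stronger readings are tempting but not supported:

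- *Patients with nothing withdrawn will raise the aspirin response, with large losses of power.* Neither their share nor their response rate is in the documents. Section C's argument that background drugs raise comparator response names mycophenolate, azathioprine, methotrexate and corticosteroids; patients must agree to stop background immune suppressants. A patient on no DMARD retains nothing, and omitting the steroid could lower response. Any power loss computed from such a mixture is illustrative only.
- *Keeping hydroxychloroquine contradicts the trial's question.* The Abstract asks about "efficacy of dipyridamole in the prevention of flares in SLE patients after withdrawal of background immunosuppressive medications", and the hydroxychloroquine exception is stated openly. BOLD may have had the same rule.
- *The unstratified comparison is biased.* It is not. Chance imbalance is possible, but the likelihood depends on an unknown share: if 10 of 50 patients had nothing withdrawn, the arms would differ by 20 points or more about 7% of the time; if 15 of 50, about 22%. Pooling all eligible patients is a legitimate choice.

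**Conclusion.** The point holds in this form. The stated identity with BOLD conflicts with the protocol's own rules on steroids, hydroxychloroquine and entry, so the passages must be reconciled. The direction and size of any resulting shift in the aspirin rate are unknown. Independently, 31 completers do not establish a 5% ceiling, and the basis of the 0 to 10% range is not given. Power of about 80% is not delivered across the plan's own assumptions: it is 0.57 at 35% vs 10% and 0.70 at 40% vs 10%.

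These power figures need no assumption about how many patients have nothing withdrawn. They rest on 25 per arm, two-sided alpha of 0.05 and the approximation that reproduces the table. The plan does not name its test; Fisher's exact test would give less (0.70 rather than 0.77 for 35% vs 5%, and 0.45 rather than 0.57 for 35% vs 10%). The interval limits assume that all 31 completers form the denominator.

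**What to change.** In section E, Power/Sample size calculation:

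1. Replace the claim of identity with a statement of the differences: steroid injection and taper optional, hydroxychloroquine continued, and some patients possibly with nothing to withdraw. Say how BOLD handled each.
2. Replace the 5% ceiling with the BOLD responder count, its denominator and its exact 95% interval.
3. State power as a range over that interval for Aggrenox rates of 35 to 50%, including 35% vs 10% and 40% vs 10%, and name the test and its sidedness.

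BICLA response by whether any drug was withdrawn at week 0 may be added as a descriptive table. Stratifying the randomisation on that factor is optional: with 50 patients and unknown prevalence its value is debatable, and stratum estimates would be imprecise.

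The cost is protocol and SAP wording, with no extra patients or procedures. The downside is a less favourable power statement.

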Only certain SLE subgroups or organ systems may respond to a particular agent, an important consideration for early phase trials. Concurrent use of immunosuppressive medications, like mycophenolate mofetil, azathioprine, methotrexate and corticosteroids, creates further biologic variability in an already heterogenous disease and confounds the interpretation of data in human studies, since these medications might interfere with or confound the mechanism of the agent(s) studied. This practice also increases the response in the comparator arms, limiting the possible differences between treatment and placebo in SLE clinical trials, necessitating the prolonged study of larger patient numbers for adequate power, and further compromising the clinical interpretability of results. Withdrawal of background immune suppression has been considered as an option to limit study time and patient exposures to untested therapies, but the community has been concerned about its safety. The BOLD (Biomarkers of Lupus Disease) trial, in which a brief course of parenteral steroids is utilized to induce a state of remission or low disease activity while background medications are withdrawn, has shown evidence this approach is safe and effective (11). Time to first flare averaged 72 days (CI 43–91), with 100% of the patients flaring by 24 weeks.

In the BLISS trials of belimumab in SLE the systemic response index (SRI), a composite measure of disease activity, was used as the primary endpoint. SRI is a landmark index defined as the composite of ≥ 4 point reduction in total SLEDAI score, with no new BILAG A or no more than one new BILAG B domain score and no more than 10% worsening in physician's global assessment (PGA), compared to baseline. Another composite measure, the SRI-BILAG (BICLA) has been used in the EMBLEM phase II trial of epratuzumab in SLE. BICLA requires the achievement of BILAG-2004 improvement (BILAG A to B/C/D, BILAG B to C/D, and no BILAG worsening), along with no deterioration in SLEDAI total score and no more than 10% worsening in PGA. In the BOLD study, BICLA was found to be more sensitive to change than SRI, when anchored to the simpler BOLD improvement criteria (drop of \geq one BILAG grade or ≥ 4 SLEDAI points) anchored to the clinician's determination of significant clinical improvement (11).

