Data will be collected by study personnel who will be kept blinded to treatment assignments. A trained study coordinator will provide data monitoring and quality assurance checks on the database. The final data will be pooled and analyzed by the investigators.

E. Statistical methods

The primary analysis will be an intention-to-treat two by two table.

Primary endpoint: A two by two table analysis of rate of response by the BICLA response index at week 24 compared to baseline (week 0) in patients on aspirin versus Aggrenox regimens, with non-response attributed to patients who receive defined non-responder treatments and/or withdraw early. Please see below for power calculations based on expected response rates. Independent predictors of BICLA response, including baseline biomarkers, biomarker responses to Aggrenox treatment, demographics and amount of steroids administered, will be further investigated by exploratory logistic regression modeling.

Secondary endpoints: Flare rates at week 24 compared between completers among treatment groups. Time to flare (log rank test). SRI 4/5 at week 24, BICLA and SRI 4/5 at each month. HRQOL comparing treatment groups versus baseline at week 24 and at each month. Although our primary endpoint is based on the BICLA response, an accepted outcome for lupus clinical trials which serves as a pilot response indicator for future trials, it is likely that some secondary endpoints, such as time to flare will be more sensitive, and more likely to achieve significance in a pilot study.

Exploratory endpoints: SRI component analyses and CLASI responses. Refinement in BICLA and SRI analysis using a propensity score derived by multiple potential confounders identified in exploratory single variate analysis. Relation of clinical and biologic endpoints with heart rate variability measures by multivariate analysis.

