An absolute difference of ≥ 12 to 15% in the response rate is however considered clinically significant in other lupus trials. Since this is a pilot study, a clinically significant (12% or greater absolute difference), but not statistically significant difference, might be considered justification for a larger study. Even if this pilot study does not reach statistical significance, the proposed exploratory biomarker studies evaluating T and B cell phenotypes, T/B cell functional studies, gene expression or serum cytokine/chemokine profiles might be used to refine the entry criteria and biologic treatment goals for a further study and/or underscore the rationale for an expansion of this study for more power of discrimination. Finally, the BICLA and other flare analyses will be performed at each monthly visit, increasing the likelihood of finding differences, should they exist, when including these secondary analyses.

An interim analysis will be performed after 20 patients will have completed the study, and will be used to assess the quality of the data collected and the treatment effects. Consideration of sample size changes can be discussed at that time.

F. Gender/Minority/Pediatric Inclusion for Research

Participants will be age 18 or older. Race, minority status and gender will not affect enrollment.

G. Human participants

The study population will include male/female patients with SLE, of age 18 or older and of all races.

Inclusion Criteria:

1. Patients with SLE meeting the ACR Classification Criteria (19)
2. Males or females, age 18-70
3. Evidence of positive ANA or anti-dsDNA within one year of screening
4. SLEDAI ≥ 4 or ≥ 1 BILAG B or A at screening, despite standard of care

Exclusion Criteria

1. WBC $< 2,000/\text{mm}^3$, lymphocytes $< 300/\text{mm}^3$ (last known labs)
2. AST or ALT > 3 times above normal cut off values (last known labs)
3. Acute lupus nephritis defined as class II, III, IV or V nephritis diagnosed within 6 months or prot/creat > 1.5 gm/gm due to active lupus or in process of receiving induction therapy for nephritis
4. Active CNS lupus affecting mental status
5. Pregnancy or breast feeding
6. Current requirement for anticoagulation
7. Contraindication to aspirin or dipyridamole, including history of recent or severe GI bleeding, hemoglobin < 9 mg/dL, platelet count of $< 30,000/\text{mm}^3$ or unstable platelet count (last known labs)

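### Does the claim of about 80% power fail because it does not hold at the 10% upper end of the plan's aspirin range?

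*Combined protocol and SAP*

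**What the plan says.** All of this is in the combined protocol and SAP.

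- **Control rate.** Section E, under Power/Sample size calculation, draws on the earlier BOLD study: "To date we have analyzed data from 31 patients who completed the BOLD protocol". From these it infers that "no more than 5% achieves a BICLA response at week 24 (range 0-10" per cent).
- **Power claim.** The next sentence assumes a "35 to 50% response rate in the Aggrenox group at week 24, a sample size of 50 patients will provide a power around 80" per cent, at a significance level of 0.05.
- **Table.** It is introduced by "By these settings and assumptions, the following power estimates are obtained". With 25 per arm it lists seven Aggrenox/aspirin pairs: 60/20, 55/15, 50/10, 45/10, 40/5, 35/5 and 35/3. The stated powers are 0.84, 0.86, 0.89, 0.80, 0.86, 0.77 and 0.84.
- **Analysis.** Section E opens with "The primary analysis will be an intention-to-treat two by two table". It names neither the test nor the sidedness.
- **Supporting evidence.** Section C reports the source study "with 100% of the patients flaring by 24 weeks".
- **Use of the result.** Later in section E, a difference of at least 12 percentage points that misses significance "might be considered justification for a larger study". After the interim analysis at 20 completers, "Consideration of sample size changes can be discussed at that time".

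**The concern.** The sentence gives one power figure for the whole 35 to 50% Aggrenox range and does not say which aspirin rate it assumes. The plan allows aspirin response up to 10%, but the table sets 10% only against the two higher Aggrenox rates in that range. Aggrenox rates of 35% and 40% appear only beside 5% or 3% aspirin. A reader could conclude that 50 patients give roughly 80% power anywhere in the stated ranges.

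If the truth were 35% against 10%, the chance of missing the effect would be about 43%, not 20%. The control rate also rests on only 31 patients, so 10% cannot be dismissed out of hand. At stake would be a trial less able to detect its target effect than its readers believe, and an interim discussion of sample size that starts from too favourable a figure.

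**Working it through.** **Inputs (section E).** n = 25 per arm; alpha = 0.05; Aggrenox response p1 = 35 to 50%; aspirin response p2 of 5% or less, range 0 to 10%. Early withdrawals count as non-responders, so n stays at 25.

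**Formula.** The plan names none. The one that fits the table is the pooled two-sided normal approximation. With p̄ = (p1 + p2)/2,

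power = Φ{ [p1 − p2 − 1.96·√(2p̄(1 − p̄)/25)] / √([p1(1 − p1) + p2(1 − p2)]/25) }.

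**Step 1: reproduce the table.**

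| Aggrenox/aspirin (%) | Stated | Computed |
|---|---|---|
| 60/20 | 0.84 | 0.845 |
| 55/15 | 0.86 | 0.866 |
| 50/10 | 0.89 | 0.895 |
| 45/10 | 0.80 | 0.811 |
| 40/5 | 0.86 | 0.865 |
| 35/5 | 0.77 | 0.772 |
| 35/3 | 0.84 | 0.844 |

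All agree within about 0.01. The one-sided, unpooled, arcsine, continuity-corrected and exact versions tried do not fit the table as a whole.

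**Step 2: the whole Aggrenox range at 5% and 10% aspirin.**

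Worked case 35/5: p̄ = 0.20; pooled SE = √0.0128 = 0.1131; unpooled SE = √0.0110 = 0.1049; (0.30 − 1.96 × 0.1131)/0.1049 = 0.746; Φ = 0.772.

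Worked case 35/10: p̄ = 0.225; pooled SE = √0.01395 = 0.1181; unpooled SE = √0.0127 = 0.1127; (0.25 − 1.96 × 0.1181)/0.1127 = 0.164; Φ = 0.565.

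| Aspirin | Aggrenox 35% | 40% | 45% | 50% |
|---|---|---|---|---|
| 5% | 0.77 | 0.87 | 0.93 | 0.97 |
| 10% | 0.57 | 0.70 | 0.81 | 0.89 |

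The table leaves out two unfavourable pairs (35/10 and 40/10) and two favourable ones (45/5 and 50/5). It is incomplete, but not tilted one way.

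**Step 3: where power crosses 0.80.** The highest aspirin rate that keeps 0.80 is about 4.3% at Aggrenox 35%, 7.1% at 40% and 10.4% at 45%.

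**Step 4: how large the weak corner is.** Spread pairs evenly over Aggrenox 35 to 50% and aspirin 0 to 10% (an illustrative weighting, not the plan's). About 81% of pairs reach 0.80, about 89% reach 0.75, about 6% fall below 0.70, and mean power is 0.88.

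**Step 5: what 31 patients can exclude.** The plan gives no responder count; 5% or less of 31 means 0 or 1, since 2/31 = 6.5%. For 0 of 31, the exact two-sided 95% upper limit is 1 − 0.025^(1/31) = 11.2%, and the one-sided 95% limit is 1 − 0.05^(1/31) = 9.2%. For 1 of 31, the two-sided limit is 16.7%.

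**The case for a change.** The strongest case for a change is that the shortfall lies inside ranges the plan itself prints. The plan tabulates 10% aspirin twice, so it treats that rate as plausible. The gap also does not need the extreme corner: at Aggrenox 35%, aspirin at 7% already gives 0.69. Against 10% aspirin, 80% power would need 43 per arm at 35% and 32 per arm at 40%, above the 25 available. The source data do not clearly rule out 10%, and qualifying the sentence would cost almost nothing.

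The figures stand, and so does the remark that the sentence leaves its aspirin rate unstated. The inference that the claim is wrong does not. The sentence comes directly after a working rate of 5% or less, and the natural reading attaches it to that rate; 0 to 10% is a bracketed range around it. The plan does not hide the weakest case at that rate, since the table prints 0.77 for 35/5. It also prints 0.80 for 45/10, so any reader can see that a lower Aggrenox rate against 10% aspirin must fall below 80%. Whether the 31 patients exclude 10% depends on the unstated count and on the choice of limit, while the report that every patient flared by 24 weeks points to the low end.

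**Conclusion.** The concern does not call for a change. At the plan's working aspirin rate of 5%, power is 0.77 to 0.97 over the stated Aggrenox range, and lower aspirin rates raise it, so a description of around 80% is fair and at most points conservative. The published entries are sound; the largest departure is 45/10, printed as 0.80 against a computed 0.81.

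What remains is an unstated condition and two sensitivity columns that any statistician can fill in from the table: 0.57 at 35/10 and 0.70 at 40/10. Supplying them would leave the number of patients, the primary analysis and every decision rule as they are. The trial is presented as a pilot whose non-significant result may still support a larger study, and sample size is already open for discussion at the interim. The amendment of January 2015 also interrupts the randomised part for the time being.

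This conclusion assumes that the pooled two-sided approximation, inferred from its fit to the table, is the method behind it, and that the power sentence refers to the 5% working rate stated just before it.

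### Monthly BICLA, SRI-4 and SRI-5 comparisons are offered as a way to find differences with no multiplicity rule, and the chance of at least one false positive among them is roughly 0.15 to 0.60

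*Combined protocol and SAP*

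**What the plan says.** Section E (Statistical methods) names one primary test: "The primary analysis will be an intention-to-treat two by two table", applied to BICLA response at week 24. The form of the test (Fisher or chi-square) is not given.

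The secondary endpoints in the same section include "SRI 4/5 at week 24, BICLA and SRI 4/5 at each month". I read SRI 4/5 as two indices, SRI-4 and SRI-5. The section then says that some secondary endpoints, "such as time to flare will be more sensitive, and more likely to achieve significance in a pilot study".

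The end of the Power/Sample size calculation adds that "the BICLA and other flare analyses will be performed at each monthly visit, increasing the likelihood of finding differences, should they exist". The same sentence goes on to describe these analyses as secondary.

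An alpha appears only in the power calculation: "a sample size of 50 patients will provide a power around 80% at a significance level of 0.05 at week 24". No alpha is given for the monthly comparisons. There is also no adjustment, order of testing, key secondary endpoint or descriptive label.

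**The concern.** The sentence in the power section states only the benefit of repeated looks, namely more chances to detect a real effect. The same looks give more chances of a significant result when there is no effect, and the plan does not say how such a result is to be read. Together with the statement that secondary endpoints are more likely to reach significance, this leaves open which of many results would count as a finding. At stake is what the trial can conclude from one significant month among many. In a pilot meant to inform a larger study, such a result could easily be given more weight than it can bear.

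**Working it through.** **Inputs from the documents**
- Allocation (section D): "Patients will be randomized 1:1 to Aggrenox" or aspirin. The power table uses 25 per arm.
- Visits with disease activity scores (section D): "week 4 and every 4 weeks until the completion of the study at week 24", that is weeks 4, 8, 12, 16, 20 and 24, so six.
- Indices: BICLA, SRI-4 and SRI-5. 6 × 3 = 18 comparisons. Without the week-24 BICLA primary, 17 are secondary. Monthly quality-of-life comparisons are not counted.
- Aspirin BICLA response: at most 20% at week 16 and at most 5% at week 24 (range 0-10%).
- Patients treated for a flare stay non-responders (section D). Time to first flare averaged 72 days in the earlier withdrawal study (section C).

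**Assumed:** 0.05 for each comparison, a 2×2 test each time, the correlations between visits and between indices, and the response rates at the other visits.

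**1. The plan's own power table** ("Power calculations for a 50 patient study, if alpha=0.05 with response rates"). Two-sided test with pooled variance and no continuity correction, n = 25 per arm, p̄ the mean of p1 and p2:

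power = Φ{ [ |p1 − p2|·√n − 1.96·√(2p̄(1 − p̄)) ] / √(p1(1 − p1) + p2(1 − p2)) }

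For 60% v 20%: (0.4 × 5 − 1.96 × √0.48) / √0.40 = (2.000 − 1.358) / 0.632 = 1.015, so power is 0.845.

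| Aggrenox v aspirin | Stated | Pooled | Fisher |
|---|---|---|---|
| 60 v 20 | 0.84 | 0.845 | 0.788 |
| 55 v 15 | 0.86 | 0.866 | 0.800 |
| 50 v 10 | 0.89 | 0.895 | 0.833 |
| 45 v 10 | 0.80 | 0.811 | 0.723 |
| 40 v 5 | 0.86 | 0.865 | 0.822 |
| 35 v 5 | 0.77 | 0.772 | 0.704 |
| 35 v 3 | 0.84 | 0.844 | 0.806 |

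The table is reproduced. It matches an uncorrected two-sided test, which hints at the intended analysis but does not specify it.

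**2. Independent tests, no effect:** 1 − 0.95^m.
- m = 6 (BICLA only): 0.265
- m = 17: 0.582
- m = 18: 0.603

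**3. Correlated tests, each of exact size 0.05,** equal correlation r between the test statistics:

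| r | 0.1 | 0.3 | 0.5 | 0.7 | 0.8 | 0.9 |
|---|---|---|---|---|---|---|
| 6 tests | 0.262 | 0.241 | 0.208 | 0.165 | 0.139 | 0.109 |
| 18 tests | 0.588 | 0.510 | 0.396 | 0.277 | 0.216 | 0.150 |

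**4. Actual size of one 2×2 test at 25 per arm.** Neither test has size exactly 0.05.

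| True rate | 5% | 10% | 20% | 30% | 40% | 50% |
|---|---|---|---|---|---|---|
| Fisher | 0.001 | 0.009 | 0.022 | 0.023 | 0.030 | 0.033 |
| Chi-square, uncorrected | 0.020 | 0.049 | 0.055 | 0.054 | 0.060 | 0.065 |

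**5. Simulated 2×2 tables, no effect, all 18 tests.** SRI-5 is nested in SRI-4, because a fall of at least 5 SLEDAI points includes a fall of at least 4.
- With assumed response rates and no permanent non-response: Fisher 0.19-0.34, chi-square 0.38-0.58.
- A separate null simulation, also nested: Fisher 0.16-0.24, chi-square 0.36-0.49.
- With permanent non-response after flare, exponential time to flare with mean 72 days, and an assumed 70% response rate at each visit among patients who have not flared. Response then falls from about 48% at week 4 to 7% at week 24:

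| Visit / index correlation (latent) | Fisher | Chi-square |
|---|---|---|
| 0.3 / 0.3 | 0.190 | 0.430 |
| 0.5 / 0.6 | 0.177 | 0.399 |
| 0.8 / 0.8 | 0.154 | 0.357 |
| 0.95 / 0.9 | 0.139 | 0.315 |

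**6. For comparison.** Bonferroni (0.05/18 = 0.0028 per test) keeps the rate at or below 0.05, about 0.036 at r = 0.5. One per-patient summary test over visits held about 0.05 in simulation.

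**The case against.** The strongest reply is that this is a pilot with one prespecified primary test, and the plan labels the monthly analyses as secondary. That stands. A reader might infer that the trial's overall type I error is inflated, or that a significant month could stand in for the primary. The documents support neither. The week-24 BICLA test keeps its own error rate, and nothing makes a monthly result a substitute for it.

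The practical consequence is also limited. The power section already allows a non-significant absolute difference of 12% or more to justify a larger study, so that decision does not need a monthly p-value. Removing monthly p-values leaves that route open. What remains is the weight an isolated significant month may carry in the trial's conclusions, and the plan itself offers repeated looks as a route to a positive finding.

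A third objection concerns the size. A model that lets patients regain response and treats the three indices as exchangeable gives 0.23 to 0.57, and a reader might take that as the figure. Under the permanent non-responder rule with SRI-5 nested in SRI-4, both ends are too high (0.14-0.19 with Fisher, 0.32-0.43 with chi-square). No narrow figure can be derived from the documents.

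A reader might also take section E to call time to flare the most sensitive endpoint. It offers it only as an example of a more sensitive one.

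Finally, the January 2015 amendment temporarily interrupts the randomized part and adds an uncontrolled group B. The point applies only to group A.

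**Conclusion.** The concern holds for group A in a limited form. The plan sets up 18 between-arm responder comparisons over six visits, 17 of them secondary, and presents them as raising the likelihood of finding differences, with no multiplicity rule or descriptive label. With no drug effect and 0.05 per comparison, the chance of at least one significant result is roughly 0.15 to 0.60: about 0.15-0.35 with Fisher and 0.3-0.6 with uncorrected chi-square. The position in that range depends on correlations, response rates and a choice of test that the documents do not give. Every 18-test scenario tried was well above 0.05. This concerns the interpretation of secondary results and leaves the validity of the primary test intact.

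**What to change.** - Replace the sentence on monthly analyses in the power section, and mark the matching entry under Secondary endpoints. State that monthly BICLA and SRI results are descriptive, given as rates and between-arm differences with confidence intervals, with no significance claim for a single month. Changing the power section alone would leave the monthly endpoints listed without a status.
- Name time to first flare, for which a log-rank test is already planned, as the one key secondary test.
- If a test over visits is wanted, use one per index that suits sparse late responses: for example a permutation test on the number of visits in response, or a GEE logistic model with a small-sample correction. An uncorrected GEE is doubtful with 25 per arm and expected aspirin response of 0-10% at week 24. A common treatment effect could also dilute an effect that appears late.

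The cost is analysis wording only; visits, data collection and sample size do not change. The downside is that an isolated monthly p-value can no longer be claimed as a finding.
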